#### **Power Analyses**

Power is the probability to detect statistically significant results from a sample, if one actually exists in the population. In order to determine the sample size needed for adequate power, we are using an alpha (criterion of significance) of 0.05 in a two-tailed (non-directional) test (Figure) as our primary outcome is the pain index score.

Since there isn't a pilot study or previous work to base the assumptions of the power analysis, 216,000 simulations were performed varying sample size ( $n=100,150,200$ ), standard deviation of the population ( $\sigma=1,3,5$ ), and assumed true difference in population means of the pain index score (24 differences ranging from 0.1 to 4.7). For each combination of sample size, population standard deviation, and difference in population mean, 1000 simulations were tested. The results for these simulations are displayed graphically in Figure 1. The power analysis was calculated for soft versus hydrophobic stents.

Because of the uncertainty of the assumptions of the power analysis, it is recommended to perform an interim analysis at  $N=100$ . If there is low variability in the populations or if the true difference of the population is greater than 3 (or some combination of the two), 100 samples would potentially provide ample power to detect the differences in the populations.

Figure 1.

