### Planned Statistical Analysis

We will evaluate parameters, including stent composition, and outcomes including complications, hematuria, pain medication requirements, return to work/normal activities, subjective assessments of pain, discomfort and satisfaction, and factors associated with stent removal, including periprocedural discomfort, and need for early/delayed removal of the stent. We will use t-test, U-test, ANOVA, chi-squared tests, and multivariate statistical methods to evaluate our outcomes.

After 100 patients are accrued, an interim analysis will be performed in order to determine if the research questions are statistically significant at the 0.05 level. If they are significant results, patient enrollment will end. If they are not significant, a second power analysis will be performed to determine if 100 more patients would provide reliable statistical power of achieving significant results. This power analysis will be much more informative as there would be actual estimates of the populations of interest. If it is determined that an additional 100 more patients would still be unlikely to yield statistically significant results, patient enrollment will end. If it is determined that an additional 100 patients would be likely to yield statistically significant results, an additional 100 patients will be enrolled into the study.

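### The interim test at 100 patients uses the whole two-sided 0.05 and a second test may follow at 200, so the trial does not hold its stated alpha

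*Combined protocol and SAP*

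**What the plan says.** Power Analyses sets the error rate, "we are using an alpha (criterion of significance) of 0.05 in a two-tailed (non-directional) test", and states that "our primary outcome is the pain index score". It recommends an interim analysis at 100 patients because the power assumptions are uncertain.

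Planned Statistical Analysis then gives the decision rule:

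- **Timing and level:** once 100 patients are in, "an interim analysis will be performed in order to determine if the research questions are statistically significant at the 0.05 level".
- **If significant:** "If they are significant results, patient enrollment will end".
- **If not significant:** "a second power analysis will be performed to determine if 100 more patients would provide reliable statistical power of achieving significant results". If success is judged unlikely, enrolment ends. If it is judged likely, "an additional 100 patients will be enrolled into the study".

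The section lists t-tests, U-tests, ANOVA, chi-squared and multivariate methods. It names no group-sequential boundary, alpha-spending function or combination test. It gives neither the level nor the form of the analysis at 200 patients, and no numerical threshold for extending. Study design and Day 0 (Stent Insertion) describe a trial of 100 patients, 50 per arm, and do not mention the possible second hundred.

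**The concern.** A significant result at 100 patients stops the trial at an unadjusted 0.05, so the first look alone uses the entire error allowance. Extending after a non-significant result, in order to try again, adds a second route to a false positive. The sum must exceed 0.05 whatever level the second test uses, unless that second test can never take place.

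What is at stake is the primary comparison of the two stents on pain. A significant result from this procedure would be reported as meeting a 5% standard that the procedure does not meet, and the final p-value could not be read at face value. A boundary chosen after the interim data have been seen would be data-driven, so the repair has to come before the interim.

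**Working it through.** **Inputs from the document**

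- Alpha 0.05, two-sided (Power Analyses).
- Interim at 100 patients, tested at 0.05 with an efficacy stop; possible extension by 100 (Planned Statistical Analysis). The maximum is 200 and the interim information fraction is 100/200 = 0.5.
- Allocation 1:1 (Study design; Day 0).
- SD scenarios 1, 3 and 5, and differences from 0.1 to 4.7 (Power Analyses).

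**Assumptions where the document is silent**

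- The final test pools all 200 patients at two-sided 0.05, the only alpha stated.
- One primary endpoint and no dropout.

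**Step 1: the plan's own figure.** A single test with critical value 1.96 gives 2 × P(Z > 1.96) = 0.0500. The stated alpha is reproduced for one look only.

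**Step 2: two looks, every non-significant interim extended.** Let Z1 be the interim statistic and Z2 the pooled final statistic. Under the null they are standard normal with correlation √(100/200) = 0.707.

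Overall alpha = P(|Z1| ≥ 1.96) + P(|Z1| < 1.96 and |Z2| ≥ 1.96) = 0.0500 + 0.0331 = **0.0831**

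A simulation of 400,000 null trials, using two-sample t-tests at 50 and then 100 per arm, gave 0.0833.

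**Step 3: extension only if the second stage looks promising.** Under the current trend, conditional power at an interim value z1 is Φ((√2·z1 − 1.96)/√0.5). Requiring at least γ means extending only when |z1| lies between (1.96·√2 + z_γ)/2 and 1.96, where z_γ is the standard normal γ quantile.

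| Conditional power required | Lower limit for \|z1\| | Added error | Overall alpha |
|---|---|---|---|
| none (always extend) | 0 | 0.0331 | 0.0831 |
| 10% | 0.745 | 0.0276 | 0.0776 |
| 20% | 0.965 | 0.0242 | 0.0742 |
| 50% | 1.386 | 0.0150 | 0.0650 |
| 80% | 1.807 | 0.0039 | 0.0539 |
| 90% | 2.027 (above 1.96) | 0 | 0.0500 |

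**Step 4: the power analysis read as ordinary power of 200 patients at the observed effect.** The lower limit becomes (1.96 + z_γ)/√2.

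- 50% required: limit 1.386, overall alpha 0.0650.
- 70% required: limit 1.757, overall alpha 0.0552.
- 80% required: limit 1.981. This exceeds 1.96, so no non-significant interim can qualify and alpha stays at 0.05.

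**Step 5: boundaries that hold 0.05.** Solving the Step 2 expression for an overall 0.05 gives:

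- O'Brien-Fleming: |Z| 2.797 then 1.977, that is p<0.0052 then p<0.048.
- Pocock: |Z| 2.178 at both looks, p<0.0294.

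**Step 6: power at the first look.** With 50 per arm, SD 5 and difference 3, the noncentrality is 3/(5·√(2/50)) = 3.0. The noncentral t distribution gives 0.844 at 0.05, 0.784 at 0.0294 and 0.558 at 0.0052.

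**The case against.** The strongest reply is that 8.3% is not the rule as written. The plan extends only when further patients are judged likely to produce significance. If likely means at least 50%, the overall error is 6.5%, and stricter readings bring it closer to 5%. On one ordinary reading, 80% power of 200 patients at the observed effect, the extension could never be triggered and alpha would be intact. The final test is also inferred: the plan does not say how or at what level the 200 patients would be analysed. Finally, this is a single-centre comparison of two standard-of-care stents, so an excess of around 1.5 percentage points might be thought minor.

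Much of this stands as a limit on size. The figure of 8.3% is a ceiling for pooled testing at 0.05, and the excess depends on a threshold that the plan never gives.

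It does not remove the defect. No 80% threshold is written, and adopting one of that kind would make the extension clause empty. The unstated final level does not help either, since the first look has used everything. The statements of 100 patients elsewhere do not cancel the explicit provision for 200.

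**Conclusion.** The concern holds. As written, the procedure exceeds its stated two-sided 0.05 whenever extension is possible; that conclusion needs no assumption about the second test beyond its being able to reject.

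The size does rest on assumptions: a pooled final test at 0.05, one primary endpoint, no dropout, and an extension rule that is followed as a binding rule. On that basis the overall error is 8.3% at most. It is about 6.5% if extension requires an even chance of success and 5.4% at 80% conditional power. The plan also refers to research questions in the plural and lists many outcomes; any inflation from that is not included here.

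This needs correcting before the interim data are examined, because it concerns the error rate of the primary comparison.

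**What to change.** State in Planned Statistical Analysis a two-look group-sequential design for the pain index score with overall two-sided alpha 0.05:

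- **O'Brien-Fleming:** stop for significance at 100 patients only if p<0.0052; test all 200 at p<0.048.
- **Pocock:** p<0.0294 at each look.

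Both hold 0.05 whether or not the extension rule is followed. Add a numerical threshold for extending, and say that the final analysis pools all 200 patients. Restate the claim of ample power at 100 patients at the chosen level. Reconcile the 100-patient and 50-per-arm statements in Study design and Day 0 with a maximum of 200.

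The alternative is to remove the extension and test once at 100 patients. That single 0.05 test is valid and keeps the 84% power at SD 5 and difference 3, but gives up the chance to enlarge the trial.

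**Cost.** The text changes are short. In the same scenario, first-look power falls from 84% to 78% (Pocock) or 56% (O'Brien-Fleming), but a test of 200 patients at the final level has about 98% or 99% power. The maximum stays at the 200 already allowed, but the trial would go on to 200 more often. By normal approximation, with every non-significant interim extended, the chance of continuing rises from about 15% to 21% (Pocock) or 42% (O'Brien-Fleming). Expected enrolment, 100 + 100 × that chance, rises from about 115 to 121 or 142.

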#### Day 0 (Stent Insertion)

Randomization will take place prior to the procedure. Patients will be randomized in a 1:1 ratio for stent composition, soft vs. hydrophobic, for a total of 50 patients in each cohort. To minimize selection bias, a randomization table will be developed before initiation of enrollment. Envelopes containing randomization assignments will be created, sequentially numbered and sealed. Once enrollment is initiated, randomization envelopes will be opened for each subject after informed consent is granted and study eligibility is confirmed. Subjects will be blinded to the stent assignment so their reported pain level and satisfaction is not influenced by the knowledge of the inserted stent type.

The surgical procedure for stone management will be performed via an approach consistent with current standards-of-care.

Patients will be discharged on a standard regimen, consisting of Norco, or an equivalent narcotic, tamsulosin, and docusate. Patients will not be placed on anticholinergic or phenazopyridine medications at discharge.

When clinically indicated, exchange of stent is permitted. The patient data will be evaluable so long as adherence to initial randomization stratification is maintained.

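### The decision to add 100 patients rests on a second power analysis with no stated bar, type of power or target difference; if it uses the observed difference, it only restates the interim p-value

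*Combined protocol and SAP*

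**What the plan says.** The Power Analyses section explains that there were no pilot data, so power was simulated over sample sizes of 100, 150 and 200, SDs of 1, 3 and 5, and 24 differences from 0.1 to 4.7. It names no target difference and no target power. It remarks that 100 patients might suffice where variability is low or "if the true difference of the population is greater than 3", and recommends an interim analysis at N=100.

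Under Planned Statistical Analysis, once 100 patients are accrued, "an interim analysis will be performed in order to determine if the research questions are statistically significant at the 0.05 level". A significant result ends enrolment. A non-significant one leads to a second power analysis, described thus: "This power analysis will be much more informative as there would be actual estimates of the populations of interest". The consequence is then: "If it is determined that an additional 100 more patients would still be unlikely to yield statistically significant results, patient enrollment will end". If success is judged likely, 100 more patients are enrolled.

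The test for extending is put in words only (reliable power, *likely*, *unlikely*). The section does not say whether the estimates include the observed difference or only the SD. Nor does it say whether the power is ordinary power at N=200 or power conditional on the first 100 patients.

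**The concern.** The second power analysis is run only when the interim result is not significant. If its inputs are the difference and SD observed in those same patients, its answer is fixed by the interim p-value. It looks like new evidence, but it is a p-value cut-off whose position depends on a bar and a formula that nobody has stated.

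The Power Analyses section accepts N=100 under uncertain assumptions because an informed look follows. If the look rests on the observed difference, it will end many trials whose true difference 200 patients would probably have detected. And because the bar and method are open, they would be chosen after an unfavourable result has been seen.

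**Working it through.** **Inputs from the document.** Two-sided alpha: "we are using an alpha (criterion of significance) of 0.05 in a two-tailed (non-directional) test". Outcome: "our primary outcome is the pain index score", simulated as a difference in means. Interim size: "for a total of 50 patients in each cohort". The extension adds 100, for a total of 200.

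**Assumptions, not in the document.** Equal SDs; 1:1 allocation kept; complete data; a final test on all 200 at unadjusted 0.05; power bars of 80% or 50%.

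**The plan's own figures.** 3 sample sizes × 3 SDs × 24 differences × 1000 = 216,000, as stated. For a difference of 3, SD 5 and 50 per arm: z = 3/(5 × √(2/50)) = 3.0, and power = Φ(3.0 − 1.96) = 85.1% (84.4% by noncentral t). This fits the plan's unquantified remark that 100 patients could be ample.

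**Largest difference that is still non-significant.** |t| < 1.984 on 98 df, so the observed difference is below 1.984 × √(2/50) = 0.397 SD. That is also roughly the half-width of its 95% interval.

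**Reading A: ordinary power at N=200 from the observed difference.** Power = Φ(√2·z₁ − 1.96), where z₁ is the interim statistic. At z₁ = 1.96 this is Φ(2.772 − 1.96) = Φ(0.812) = 79.2% (79.8% by noncentral t). Reaching 80% needs z₁ = (1.96 + 0.842)/√2 = 1.981, or p = 0.048, which the non-significance trigger excludes.

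**Reading B: conditional power under the observed trend, all 200 pooled.** Power = Φ(2z₁ − √2 × 1.96). At z₁ = 1.96 this is Φ(3.920 − 2.772) = 87.5%. It equals 80% at z₁ = (2.772 + 0.842)/2 = 1.807, or p = 0.071. The extension is open for p from 0.050 to 0.071.

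**Reading C: *likely* taken as more than 50%.** Both formulas give z₁ = 1.96/√2 = 1.386, or p = 0.166. The extension is open for p from about 0.05 to 0.166.

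**Power of the whole procedure.** For a true difference of d SDs the interim drift is θ = d × √25, that is 2.0 for d = 0.4 and 1.5 for d = 0.3. Overall power is P(|z₁| > 1.96) plus the probability of extending and then being significant at N=200. The fixed N=200 trial has drift √2·θ. By numerical integration:

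| True difference | Quantity | A: 80% ordinary | B: 80% conditional | C: above 50% | Fixed N=200 |
|---|---|---|---|---|---|
| 0.4 SD | Significant at N=100 | 51.6% | 51.6% | 51.6% | – |
| | Gained by extending | 0 | 5.3% | 17.5% | – |
| | Overall power | 52% | 57% | 69% | about 80% |
| | Extended | 0 | 6% | 21% | – |
| | Stopped non-significant at N=100 | 48% | 42% | 27% | – |
| 0.3 SD | Significant at N=100 | 32.3% | 32.3% | 32.3% | – |
| | Gained by extending | 0 | 4.1% | 14.5% | – |
| | Overall power | 32% | 36% | 47% | 56% |

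At SD 5, 0.4 SD is 2 points and 0.3 SD is 1.5 points, both within the simulated range. Over all true differences, the chance of extending is at most 0, 6.1% and 22.7% under A, B and C.

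**Type I error.** With both looks at 0.05 it is 5.4% under B, 6.5% under C, and 8.3% if every non-significant trial is extended.

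**The case against.** A reader might infer that the extension can never be triggered and is in effect a dead letter. The documents do not support that, for four reasons.

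- **The bar.** No 80% figure appears anywhere. The deciding words are *likely* and *unlikely*, whose plain sense is nearer 50%. At that bar up to about 23% of trials extend.
- **The type of power.** With the first 100 patients in hand, conditional power is a natural choice, and it reaches 87.5%.
- **The margin.** Under Reading A the ceiling misses 80% by 0.2 points (noncentral t) or 0.8 points (normal approximation). The interim is timed by accrual, while outcomes come later, partly by mail, and patients may skip questions. With 95 evaluable at the interim and 100 added, the ceiling is 80.2%; with 90 it is 81.3%.
- **The inputs.** The section does not expressly say that the observed difference is used. If only the SD were re-estimated, an 80% bar could be met: for an assumed difference of 3 and SD 7, power is 57.3% at N=100 and 85.8% at N=200.

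It is also fair to say that the protocol states enrolment as 100, that the extension is contingent, and that stopping for low power does not by itself bias the comparison.

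All of this stands, and it limits the claim. It does not remove it. The second power analysis is meant to replace guesses about both the SD and the difference, and no target difference is named that could be held fixed, so using the observed difference is the most natural reading. On that reading even the most generous bar examined loses 9 to 11 points against a fixed N=200.

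**Conclusion.** The point holds as a gap in specification with a measurable cost. The extension rule lacks a bar, a type of power and a fixed target difference. If the observed difference is used, the rule is an undeclared p-value cut-off. Depending on the reading, overall power is 52% to 69% at a true 0.4 SD, against about 80% for a fixed N=200, and 32% to 47% at 0.3 SD, against 56%.

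These figures depend on the assumptions listed with the calculation, above all the use of the observed difference and unadjusted 0.05 at both looks. They do not show that extension is impossible. The type I error of testing twice is a separate matter; correcting alpha would not by itself repair the basis of the extension decision. Severity: should-fix.

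**What to change.** In Planned Statistical Analysis, replace the second power analysis with a rule fixed before the interim:

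1. State the difference in pain index score worth detecting, chosen on clinical grounds, and a numeric power bar.
2. At N=100, estimate the pooled SD without reference to arm, before the arms are compared. Compute power for the stated difference at N=100 and N=200.
3. If the interim test is not significant, extend when power is below the bar at N=100 and meets it at N=200; otherwise stop. Do not use the observed arm difference in this decision.
4. Split the two-sided 0.05 across the two looks (0.025 at each is the simplest, conservative choice), and use those levels in step 2. Extending more often under two tests at 0.05 would otherwise push the type I error towards 8.3%.

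The difference should not be taken from the remark about values above 3 in Power Analyses. That remark describes when 100 patients might be enough; it is not a target. With a difference of 3 and an 80% bar at 0.05, power at N=100 already exceeds the bar at every simulated SD (85.1% at SD 5, higher at 1 and 3). The rule would then never extend within that range, and power for a 2-point difference at SD 5 would stay at about 51%.

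The cost is one paragraph of text and one clinical decision. The extension may be used more often, including when the observed difference is small, but never beyond the 200 patients already allowed. The alpha split makes stopping for significance at N=100 somewhat harder.

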## **RISKS AND BENEFITS**

The results from this study will not directly benefit the patients who agree to participate, however, we hope they will help determine if composition of a stent impacts patient comfort, satisfaction, and outcomes following stone surgery. Knowledge gained from this study may help us improve our stone management practice.

Participation in this study will not affect the patient's risks associated with the standard of care stone management procedure. Risks associated with the surgical procedure for stone management will be discussed with all participants as part of their clinical care and clinical consent for the procedure will be obtained. Patients may feel uncomfortable or embarrassed answering some of the questions on the study questionnaires. They will be instructed to skip any questions that they are not comfortable answering.

## **DATA AND SAFETY MONITORING**

Participation in the proposed study will not pose any risks to the participants beyond what is expected from the standard of care surgical stone management procedure. Data will be reviewed bi-annually to ensure there are no significant outliers. If such are noted, they will be investigated by the research team.

The PI will monitor the study for any serious adverse events (SAEs) from the time of the initial stent placement through the completion of the 7 day post stent removal questionnaires. All HRPO guidelines for reporting SAEs will be followed. Should there be a serious adverse event that occurs related to the proposed protocol that increases the risks to the participants, the study will be stopped, an investigation will be conducted, and a findings report will be generated before the study is resumed.

**Table 1: Schedule of Study Procedures and Assessments from Screening to Post-Stent Removal**

	Screening Visit (Up to 28 days before surgery)	Day 0 (Stent Insertion)	Stent Removal	Day 7 (± 1 Day) Post Stent Removal
Informed Consent	X			
Demographics	X			
Medical & Surgical History	X			
Height & Weight	X			
Incl./Excl. Criteria Confirmation	X	X		
Randomization		X		
Procedure Data Collection		X	X	
Satisfaction Questionnaire			X	X
Analog Pain Scale	X			
AUA Symptom Score	X		X	X
Imaging Data			X	
USS Questionnaire 1 (stent in situ)			X	
USS Questionnaire 2 (post stent)				X
Adverse Events		X	X	X

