#### **Baseline**

Once informed consent for study participation is obtained, patients will be asked to complete:

- AUA Symptom Score Questionnaire
- Analog pain scale

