#### At the Time of Stent Removal

The participants will be asked to complete the following questionnaires prior to stent removal:

- Ureteric Stent Symptoms Questionnaire 1 with Analog Pain Scale included (USSQ 1 stent in situ)
- AUA Symptom Score Questionnaire
- Satisfaction Questionnaire

In addition, the patients will be asked to share with us the number of days pain pills have been taken, and their compliance with tamsulosin and docusate. We will assess for any use of anticholinergics, other analgesics and antibiotics.

The participants will then undergo cystoscopic removal of the stent in clinic.

Results of any standard of care imaging obtained prior to stent removal will be collected.

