## Day 7 Post-Stent Removal

On day 7 post stent removal, participants will be asked to complete:

- Ureteric Stent Symptoms Questionnaire 2 with Analog Pain Scale included (USSQ 2 post stent)
- AUA Symptom Score Questionnaire
- Satisfaction Questionnaire

Copies of the surveys along with addressed and stamped envelopes will be given to the participants at the time of office visit for stent removal. Surveys will be self-administered at home and mailed back to the research center. Reminder phone calls will be made to the participants to assure compliance.

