## ***Outcome measures***

1. Stent
  - a. Type
  - b. Composition (soft or hydrophobic)
  - c. Length
2. Stent complications
  - a. Migration
  - b. Malposition
  - c. Dislodgement
  - d. Need for re-insertion
3. Time to stent removal
  - a. Clinically planned or required due to symptoms
4. Health Related Quality of Life
  - a. Ureteric Stent symptoms Questionnaire 1 and 2
  - b. AUA Symptom
5. Pain Score as reported by the participants on the self-administered assessment
6. Procedure Satisfaction Questionnaire
7. Use of analgesics for pain control
  - a. documented pain prescription at the time of discharge
  - b. self-reported duration of analgesics use after stent insertion (in days)
8. Residual stone burden
  - a. KUB, U/S, CT

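### The only pre-stent pain and AUA scores may be up to 28 days old at surgery and are not repeated on Day 0, which limits precision but does not bias the comparison

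*Combined protocol and SAP*

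**What the plan says.** In Table 1, consent, the analog pain scale and the first AUA score all fall in the column headed "Screening Visit (Up to 28 days before surgery". The Day 0 column marks only eligibility confirmation, randomisation, procedure data and adverse events.

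The Baseline section fixes no day relative to surgery. It says "Once informed consent for study participation is obtained, patients will be asked to complete" two forms: the "AUA Symptom Score Questionnaire" and the "Analog pain scale".

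At stent removal the patient completes the "Ureteric Stent Symptoms Questionnaire 1 with Analog Pain Scale included (USSQ 1 stent in situ", and a week later the "Ureteric Stent Symptoms Questionnaire 2 with Analog Pain Scale included (USSQ 2 post stent". The AUA score is repeated at both visits. No USSQ is given before the stent.

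Outcome measures lists "Ureteric Stent symptoms Questionnaire 1 and 2" (item 4a), the AUA score (4b) and the pain score (item 5) without ranking them. The only ranking is in Power Analyses, "as our primary outcome is the pain index score", and no instrument or visit is given for that score. Covariate data has seven items, none of them a baseline symptom score. Planned Statistical Analysis names tests and unspecified multivariate methods, but no analysis adjusted for baseline or based on change from it.

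**The concern.** The patients have current stone disease, and their pain can plausibly change over four weeks. A score taken 28 days before surgery may say little about the patient's state when the stent goes in, while another patient's score may be only a day old. A baseline that predicts the outcome weakly removes little between-patient variation.

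Precision matters in this trial. Power Analyses says there was no earlier work on which to base its assumptions and works from guessed SDs of 1, 3 and 5. Planned Statistical Analysis then uses the first 100 patients to decide whether to stop or to enrol 100 more. A better baseline, if used, could make that decision clearer at almost no cost.

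The exclusion criteria also do not rule out a ureteral stent already in place, and no field specifically asks about one. Some baseline scores may therefore already reflect a stent.

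**Working it through.** **1. The plan's own figures.** Three sample sizes × 3 SDs × 24 differences × 1,000 runs = 216,000, as stated; differences from 0.1 to 4.7 in steps of 0.2 do give 24 values. The plan says 100 patients may give ample power if the true difference exceeds 3. Taking 100 as the total (50 per arm, as in the Day 0 section), two-sided alpha 0.05 and the largest SD, 5:

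- standard error = 5 × √(2/50) = 1.00
- power = Φ(3/1.00 − 1.96) = Φ(1.04) = 85.1% (84.4% by the noncentral t)

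That agrees with the plan's statement and makes no use of baseline.

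**2. What a baseline score can add.** Let r be the correlation between baseline and outcome. It is not in the documents, so a range is shown. ANCOVA multiplies the outcome variance by 1 − r². A change score multiplies it by 2(1 − r), if the SD is the same at both visits. With 50 per arm, SD 5 and difference 3:

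| r (assumed) | ANCOVA variance | ANCOVA power | Difference detectable at 80% power (ANCOVA) | Change-score power |
|---|---|---|---|---|
| 0 | 1.00 | 85.1% | 2.80 | 56.4% |
| 0.2 | 0.96 | 86.5% | 2.75 | 66.0% |
| 0.3 | 0.91 | 88.2% | 2.67 | 71.8% |
| 0.5 | 0.75 | 93.4% | 2.43 | 85.1% |
| 0.7 | 0.51 | 98.7% | 2.00 | 97.2% |

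For example, at r = 0.5 the standard error is √0.75 = 0.866, and Φ(3/0.866 − 1.96) = Φ(1.50) = 93.4%.

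If a fresh score has r = 0.5 and an old one r = 0.3, the repeat is worth 93.4 − 88.2 = 5.2 percentage points. If both have r = 0.3, it is worth nothing. Below r = 0.5 a change score does worse than ignoring baseline.

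**3. Validity.** In 10,000 simulated trials at each of r = 0, 0.3 and 0.6 (50 per arm, SD 5), ANCOVA had type I error of 4.7%, 5.1% and 4.8%. For a true difference of 3 the mean estimates were 2.99, 3.00 and 3.00. A weak baseline neither shifts the estimate nor inflates alpha.

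**4. Which instruments match.**

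| Instrument | Before stent | At removal | Day 7 after removal |
|---|---|---|---|
| Analog pain scale | yes | yes, within USSQ 1 | yes, within USSQ 2 |
| AUA score | yes | yes | yes |
| USSQ domain scores | no | yes | yes |

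**The case against.** The strongest reply is that nothing in the plan depends on the baseline. Allocation is randomised 1:1, and no baseline-adjusted or change-score analysis is specified. The power in step 1 needs no baseline at all. A fresher score that is never used in the analysis leaves the trial exactly where it was. All of this stands, and it is why the covariate analysis has to be part of the fix. It is also fair that 28 days is an upper limit, and that nothing in the documents shows same-day stone pain to predict stent pain better than a screening score.

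A reader might also infer more than the documents support:

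- That the baseline does not match the outcome instrument. This is true only of the USSQ domain scores. Whether the primary outcome has a matching baseline cannot be settled while the pain index score is undefined: it has one if it is the analog scale, and none if it is a USSQ domain score.
- That the USSQ is the main outcome. The outcome list does not rank its items.
- That the Day 7 USSQ would serve as the stent-free reference, so that the analysis conditions on a value measured after randomisation. No section proposes this.
- That an existing stent would go unrecorded. Medical and surgical history is collected and could capture it, although nothing requires that.

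**Conclusion.** The point holds as a low-cost improvement in precision, not as a threat to validity. The documents do allow a pain and AUA baseline anywhere from 0 to 28 days before surgery, with no Day 0 repeat. Baseline pain may thus be out of date, at an interval that varies between patients.

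The size is modest and rests on assumed correlations. In the illustration, adjustment adds 88.2 − 85.1 = 3.1 points of power at r = 0.3 and 93.4 − 85.1 = 8.3 points at r = 0.5. The part due to a fresher measurement is only the difference between the two correlations, and could be close to zero. No gain appears unless the analysis adjusts for baseline. The plan's sample size figures do not depend on this point.

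**What to change.** - In the Baseline and Day 0 sections and in Table 1, repeat the analog pain scale and the AUA score on Day 0 before the randomisation envelope is opened. Define these as baseline, with the screening value as fallback if the Day 0 form is missing.
- At the same sitting, record whether a ureteral stent is already in place (yes/no).
- In Covariate data and Planned Statistical Analysis, name the matching baseline score and prior stent (yes/no) as ANCOVA covariates for the pain and AUA outcomes, in place of change scores. This requires stating which instrument and visit the pain index score refers to.
- A pre-stent USSQ is optional. The documents label the two forms only for use with the stent in place and after its removal, so whether either suits a patient before stenting cannot be judged from them.

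The cost is a few minutes of forms on the day of surgery, at a visit that already takes place, and a few lines of amendment. The downside is slightly more burden on the patient that day.
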